No exclusions will be made due to race or ethnic background. According to the US Census Bureau [US Census Bureau, 2010] the Bergen County region of New Jersey, where Kessler Rehabilitation Institute and the outpatient Clinic are located, is made up of approximately 74% white, 16% Asians and 7% African Americans with 3% being other races. Persons of Hispanic or Latino origins represent about 16% of the Bergen County population. It is reasonable to expect similar groupings for the subjects of this investigation. If it appears that participation according to gender or race is going to be different than that of the Census data, we will actively recruit additional subjects to achieve that distribution. There is no reason to expect any differences in the results of this investigation as a consequence of race or of ethnic background.

o **Inclusion Criteria (general)**

- Age 50 to 80;
- Healthy age-matched volunteers
- diagnosis of CVA that occurred more than 5 days prior (for the stroke survivors group);
- English speakers;
- UE unilateral or bilateral involvement (from new bilateral CVA)
- motor involvement (FMA score 20 to 45);
- ability to actively move UE more than 10° for shoulder and elbow flexion/extension;
- ability to actively extend fingers at least 5°
- cognitive skills to participate (Montreal Cognitive Assessment (MoCA) [Nasreddine et al 2005] score 10-30).
- The adaptive nature of BBC system hardware and therapeutic games can compensate for the motor limitations due to other co-morbidities. Therefore potential participants will not be excluded due to co-morbidities such as Parkinson or arthritis. Subjects may have normal cognition, MCI or dementia, since the games can compensate for diminished cognition through built-in cues and instructions.

o **Inclusion Criterion for the controlled clinical trials arm at Kessler Foundation**

- Living within 25 miles radius of Kessler Foundation West Orange location. This will facilitate participation in the outpatient clinic training, which follows inpatient rehabilitation.

o **Exclusion Criteria. (general)**

- being younger than 50 or older than 80 years of age
- previous stroke
- Inability to actively extend fingers at least 5 degrees;
- Fugl-Meyer scores of 19 or less;

- severe visual neglect or legally blind
 - severe hearing loss or deafness
 - receptive aphasia or severe expressive aphasia;
 - severe spasticity (Modified Ashworth Scale 4/4)
 - contractures of the upper limb joints

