measures taken during outpatient therapy on BAC (B), and post-outpatient treatment (A).

Subject Recruitment

20 elderly 5 days or more post-CVA admitted to Kessler Institute for Rehabilitation/Kessler Foundation) for inpatient rehabilitation will be recruited. Subjects will be pre-screened through a standardized questionnaire and MoCA screening. We expect to screen at least 70 potential subjects, also trying to determine candidates who will continue outpatient rehabilitation at Kessler Foundation. Those who met inclusion criteria will be consented by [name] MD or [name] (Co-Investigators). The 20 recruited subjects will subsequently be randomised equally into an experimental group (n=10) and a control group (n=10).

We will also recruit the 20 caregivers of the experimental and control subjects. The caregivers will provide feedback on the subjects during the outpatient component of their therapy, every 4 weeks. We will be looking for changes in independence in activities of daily living, cognition and mood that the caregivers will report, as well as self-reported outcomes by the subjects. The feedback will be using the Stroke Impact Scale [Duncan et al. 2002] and the Upper Extremity Functional Index (UEFI) [Stratford 2001] standardized questionnaires, as well as free form communication with researchers.

Subject standardised evaluations for control study on early sub-acute post stroke

Both experimental and control groups will undergo standardised evaluations for motor function/impairment, cognition and emotive states. All subjects will be evaluated before, and after their in-patient rehabilitation. Those patients who transition to home rehabilitation will be evaluated again before commencing outpatient rehabilitation, while those who transition directly to outpatient rehabilitation will not. All subjects will be evaluated again at the completion of their outpatient therapy. All clinical evaluations of the control study subjects will be performed at the Kessler Kessler Foundation.

OT evaluations

An occupational therapist blinded to the treatment allocation will evaluate for motor impairment and function of both UEs. These evaluations are the following:

- Fugl Meyer Assessment (FMA)
- Jebsen test of hand function [Jebsen 1969]
- active range of shoulder, elbow and finger movement (goniometer)
- shoulder strength (wrist weights)
- range of forearm pronation/supination
- grasp strength (dynamometer)

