- pinch strength (pinch-meter)bimanual activities (Chedoke Inventory -9) [Barreca 2000]. The need to evaluate both UEs stems from the nature of BAC bimanual training and from our inclusion of subjects who may be bilaterally affected by their first CVA.

Emotional & Neuropsychological evaluations

- The neuropsychologist will perform the cognitive/emotive evaluations. We will assess
- emotive state (via the Beck Depression Inventory II)
 - verbal and visual attention (with the Neuropsychological Assessment Battery NAB)
 - processing speed (with the Trail Making Test A [Heaton 1991] - TMT)
 - verbal and visual learning and memory (with the Hopkins Verbal Learning Test, Revised (HVLTR) [Brandt 2001])
 - Brief Visuo-spatial Memory Test, Revised (BVMT-R) [Benedict 1997])
 - executive function with the Trail Making Test B (TMT-B) and the NAB Executive Functioning Module.

The initial evaluations will serve as baseline for all participants. Subsequent to the inpatient VR training, all participants will be evaluated again for cognitive and emotive state for indication of clinical benefit. Subjects who transition to home will be evaluated again at the start of their outpatient rehabilitation. All subjects will be evaluated again for cognitive and emotive state at the end of their outpatient therapy. For subjects who skip home rehabilitation and transition directly to outpatient training, the measures at discharged from inpatient rehabilitation will be considered as baseline for start of outpatient training. To minimize test learning effects we will use alternate test forms for NAB tests, as well as reliable change formulas for all other forms [Jacobsen and Truax, 1991].

Inpatient and outpatient experimental therapy for the control study at Kessler Foundation

All subjects, regardless of group randomisation, will continue their standard of care rehabilitation (physical therapy, occupational therapy, speech and language therapy and cognitive training). All subjects, regardless of randomization, will have the same duration of therapy. Specifically, subjects randomised in the control group will have an added duration of standard of care rehabilitation equal to the experimental group training duration on the BAC.

Experimental group

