In the motor domain the session will train endurance (by increasing the length of training), strength (by modulating gravity loading and lifting arm off table), motor control (by requiring patients to follow prescribed paths), and movement speed (by inducing more arm repetitions per minute).

In the cognitive domain the cognitive load will gradually be increased by moving from uni-manual play (need to control only one avatar) to bimanual play (simultaneous control of two avatars). This will train split attention, task sequencing and dual tasking, something problematic for the elderly.

Control group

10 subjects in the control group will receive their standard of care intervention during inpatient rehabilitation post CVA. To this we will add an equal duration of standard of care to the experimental therapy (progressing from 15 minutes/session in sessions 1-4 to 30 minutes during the last inpatient session). In the outpatient period they will have an added duration of customary therapy. The added therapy will progress from 30 minutes/session at start of outpatient therapy to 45 minutes/session at the end, matching the experimental group training duration on the BAC.

Control study Outcomes

Primary outcomes

The primary outcomes for both groups will be those outlines in the Feasibility Study component of the project. The main motor outcome measure will be the FMA UE score, and success will be a group average score increase of 10 points or more, compared to baseline. The main outcome for the cognitive domain will be executive function improvement measured by Trail Making Test B (TMT-B) and the NAB Executive Functioning Module.

Secondary outcomes

The secondary outcomes for both groups will be those outlined in the Feasibility Study component of the project,

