In the motor impairment domain, secondary outcomes will be increased arm range in pronation/supination (based on new games we developed), grasp strength increase, finger extension range increase, and increase in UEFI. We expect bimanual training to improve CAHAI 9 scores (by at least 6 points), reflecting more ADL independence in tasks that are requiring both arms. The progression in ADL independence will be indicative of transfer to function. Other secondary outcomes will be changes in therapeutic game scores, change in game duration (indicative of reduction in task completion time) and change in play intensity (number of arm movement repetitions/minute). Another secondary outcome will be subjective evaluation scores for ease of use of the BAC, and overall system rating.

In the cognitive domain, we also foresee the subjects will have improved focus, better verbal and visual memory. In the emotional domain, we will evaluate the depression scores as measured by the Becks Depression Inventory II standardized test. We will consider success and average group reduction of 5 points in the severity of depression.

In addition there will be supplementary secondary outcomes:

- a) Scores obtained on the Stroke Impact Scale (Version 3);
- b) feedback from the subjects during the outpatient component of therapy (only for intervention group);
- c) feedback obtained from caregivers during outpatient therapy. The caregivers for subjects in either experimental or control groups will use the same feedback forms and provide feedback at the same time points.

An additional important outcome will be the rate of motor recovery as visualized by the curves of evaluation variables obtained pre-, and post inpatient therapy, then pre-, and post- outpatient therapy. These will provide indication on the envisaged benefits from the use of the experimental device and elucidate what gains are due to natural recovery and what gains may be attributes to training on the BAC.

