- o **Data Analysis and Data Monitoring.** We will use repeated measures of ANOVA statistical analysis to look at the participants' data comparing pre-training conventional evaluation results with post-training results, to determine early indications of clinical benefit. We will also collect subjective evaluation questionnaires from each participant and from the occupational therapist (once post-training) on their impression of the system, its perceived benefits and shortcomings, its ease of use in a clinical setting. We will also collect data on Activities of Daily Living, using a standardised form, as well as data from caregivers so to gauge transfer of training to real life activities.

In order to gauge technology acceptance we will collect a subjective evaluation of the BAC from each participant in the experimental group. The scores (1 – least favourable outcome to 5 most favourable one) from each question will be averaged over the group. The BAC subjective evaluation forms will be collected twice (after 6 weeks of outpatient therapy and at end of outpatient therapy). By looking at the progression (or regression) of these scores, we will also be able to determine if ease of use of the technology increased with the accumulation of training sessions (or not).

All the data will be entered to the central data management system remotely.

- o **Data Storage and Confidentiality.** Each subject will have his/her name encoded such that the experimental and clinical measures will not log the participant's real name. The only mapping between the assigned encoded ID and the participant's real identity will be on the consent forms. These will be kept under lock by:

- 1) [name] OT and [name] for the participants early post-stroke PowerBack Rehabilitation;
- 2) [name] for the participants early post-stroke training at Kessler Foundation

The computerized data will be uploaded on a cloud secure database. Access to the database will only be granted to the research team, and will be password protected. Paper records involving the motor and cognitive evaluations as well as the subjective evaluation questionnaires will also be kept locked by [name] OT, [name], [name] (for the cognitive and emotive evaluations of the feasibility subjects) and [name] MD for the controlled trials subjects at Kessler Foundation.

- o **Transition from Research Participation.** Subjects will not have their standard of care or medication interrupted during participation.

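### The RCT analysis is stated only as a pre-post repeated measures ANOVA and names no between-arm contrast; a baseline-adjusted arm comparison would supply one and is usually more precise

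*Protocol*

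**What the plan says.** In the section Data Analysis and Data Monitoring, one sentence holds all of the protocol's inferential analysis: "We will use repeated measures of ANOVA statistical analysis to look at the participants' data comparing pre-training conventional evaluation results with post-training results". Its purpose is "to determine early indications of clinical benefit". The sentence is not limited to the RCT, and it names no group factor, group-by-time term or covariate.

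Other sections give the RCT setting:

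- **Allocation** (Randomized control study protocol, Subject Recruitment): "The 20 recruited subjects will subsequently be randomised equally into an experimental group (n=10) and a control group (n=10").
- **Baseline.** Both groups are evaluated before inpatient therapy, and under Emotional & Neuropsychological evaluations: "The initial evaluations will serve as baseline for all participants".
- **Motor success rule** (Control study Outcomes, Primary outcomes): "success will be a group average score increase of 10 points or more, compared to baseline".
- **Aim of the recovery curves** (Control study Outcomes, Secondary outcomes): to "elucidate what gains are due to natural recovery and what gains may be attributes to training on the BAC".
- **Entry range** (Inclusion Criteria, general): "motor involvement (FMA score 20 to 45").

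**The concern.** The aim of separating natural recovery from the training effect needs a comparison of the two arms. Neither the analysis sentence nor the 10-point success rule makes one. Subjects enroll from 5 days after stroke, and the protocol itself expects natural recovery, so a pre-post gain is to be expected in both arms whether or not the device works. A significant time effect, or a 10-point gain in the experimental group, would not answer the question for which the control group was recruited.

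A reader may fill the gap with the group-by-time test of the repeated measures ANOVA. That is a between-arm test, but it handles baseline by subtracting it. With only 10 subjects per arm and a 25-point entry range, chance baseline differences of several FMA points will be common, and subtraction removes them fully only if the true slope of post score on baseline is 1.

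**Working it through.** The protocol gives no alpha, power, SD, correlation or between-arm effect, so there is no figure of its own to reproduce.

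**Inputs from the protocol:** 10 per arm; entry FMA 20 to 45; success at a mean gain of 10 points.

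**Assumed inputs:** baseline FMA uniform on 20 to 45; equal SDs before and after; r from 0.3 to 0.9; two-sided 5% level; a between-arm effect of 1 SD, for illustration only.

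**1. What a pre-post test shows.** Suppose both arms recover 10 points equally and r=0.5. The SD of the change is 7.2 × √(2(1-0.5)) = 7.2. Over all 20 subjects, the mean change has SE 7.2/√20 = 1.6, so a 10-point recovery is about 6 standard errors from zero. In simulation the time effect was significant in about 100% of such trials, although the device had no effect. By symmetry, an arm whose true mean gain is 10 meets the 10-point rule about 50% of the time, whatever caused the gain.

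**2. Chance imbalance.** The SD of a uniform variable on 20 to 45 is 25/√12 = 7.2. The SE of the baseline difference is 7.2 × √(2/10) = 3.2 points. The largest SD possible on this range is 12.5, which gives 12.5 × 0.447 = 5.6 points.

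**3. What remains after subtraction.** With two visits, the group-by-time F test is the t-test on change scores. Given a baseline difference d and equal SDs, its estimate is off by -(1-r)d. ANCOVA is off by about 0.

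| r | Remaining shift for d = 3.2 | Remaining shift for d = 5.6 |
|---|---|---|
| 0.5 | 1.6 | 2.8 |
| 0.7 | 1.0 | 1.7 |
| 0.9 | 0.3 | 0.6 |

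**4. Precision.** In units of SD² × 2/n, the variance is 2(1-r) for the change score and 1-r² for ANCOVA. The ratio is (1+r)/2. Estimating the slope from 20 subjects multiplies it by 1 + 1/(2n-4) = 1 + 1/16 = 1.0625.

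| r | (1+r)/2 | × 1.0625 |
|---|---|---|
| 0.3 | 0.65 | 0.69 |
| 0.5 | 0.75 | 0.80 |
| 0.7 | 0.85 | 0.90 |
| 0.8 | 0.90 | 0.96 |
| 0.9 | 0.95 | 1.01 |

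Break-even is where (1+r)/2 = 16/17, that is r = 15/17 = 0.88. If the true slope is exactly 1, the ratio is 1.0625, a loss of about 6%.

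**5. Simulation check** (40,000 trials per setting, 10 per arm). Type I error was about 5% for both methods, and both averaged 1.00 for a true effect of 1.00 SD. Among trials with a baseline imbalance near +1 SE, the change-score estimate averaged 0.77 SD (r=0.5) or 0.86 SD (r=0.7), and ANCOVA 0.99 in both. Power for the 1 SD effect went from 56% to 65% at r=0.5, from 78% to 82% at r=0.7, and from 99.7% to 99.6% at r=0.9. The group main effect, another line of the same ANOVA table, had only 19% to 23% power. It therefore matters which term is tested.

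**The case against.** The strongest reply is that covariates belong in a statistical analysis plan, which is not shown, and that naming repeated measures ANOVA does not exclude one. This stands as far as it goes: a missing covariate alone would be no finding. But the protocol does state a method and a success rule, and as stated neither uses the control arm.

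A reader might infer that repeated measures ANOVA ignores the baseline, so that chance imbalance passes whole into a biased result. The documents and the arithmetic do not support this. Baseline is the first repeated measurement and is subtracted. Only the (1-r) share remains, with opposite sign. Over randomisations there is no bias and no inflation of type I error.

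Three further limits stand:

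- The change-score equivalence holds for two visits. The RCT has three evaluations, or four for subjects who first go home, and an omnibus group-by-time test over these is a different test. A repeated measures display also suits the recovery curves.
- The imbalance cannot be called large against the effect sought. No between-arm effect is stated, and the 10 points are a within-group gain.
- The protocol says only that allocation is equal. It does not say that allocation is simple or unstratified.

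**Conclusion.** The point holds in two parts of unequal weight. The heavier part is that the stated analysis and the motor success rule are both pre-post, while the trial's aim needs a contrast between arms; this follows from the text and needs no assumption. The lighter part is that, if a two-visit group-by-time test is what is meant, baseline-adjusted ANCOVA is usually the better choice. It removes a conditional shift of about 1.0 to 1.6 FMA points for a one-SE imbalance, and cuts variance by about 10% to 20%, at r of 0.7 to 0.5.

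These sizes rest on an assumed baseline SD of 7.2, equal SDs and the assumed r. The gain is modest: it vanishes near r = 0.88 and turns into a cost of up to about 6%. It concerns precision and accuracy given the observed imbalance. It does not make the planned method invalid. No comparable figures can be given for TMT-B or the NAB module, because the protocol gives no spread for them. The change should be made.

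**What to change.** For the RCT, replace the analysis sentence with text such as: *Each outcome measured before inpatient therapy in both arms is compared between arms at the post-inpatient and the post-outpatient evaluation by ANCOVA, with the pre-inpatient value of the same measure as covariate. The adjusted arm difference and its 95% CI are reported.*

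Keep repeated measures ANOVA and the recovery curves as descriptive supplements, and report the 10-point group gain as a description of each arm. Keep the pre-post wording for the uncontrolled components. Game scores arise only in the arm that trains on the BAC, so they remain descriptive.

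Both named evaluations are planned for all subjects, so the contrast does not depend on the pre-outpatient evaluation, which subjects who move directly to outpatient therapy do not have. The cost is a short text change and one degree of freedom, with a variance loss of about 6% if the true slope is 1. For outcomes already evaluated at these visits, no new data are needed.

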 - uncontrolled hypertension (>190/100 mmHg)
 - severe cognitive impairment determined by Montreal Cognitive Assessment (MoCA) [Nasreddine et al, 2005] test of 9 and below;
 - No chemodenervation or nerve block to upper limb involved during the experimental period (e.g., botulinum toxin injection)
 - inability to speak English;
 - a history of violence or drug abuse.
 - inability participate in the neuropsychological pre-study assessment for reliable scores (e.g., cognitive impairment, communication disorders).
- **Exclusion Criteria. (Controlled study arm)**
 - Those living outside approximately 25 miles radius of Kessler Foundation West Orange location. Those living too far will have a harder time completing the study as outpatients, as they will probably choose clinics closer to home.
 - **Vulnerable Subjects.** The targeted subjects for the feasibility arm of the study will be sub-acute phase patients at PowerBack. Those targeted from the controlled trials arm of this study will be inpatients in a rehabilitation facility who subsequently become outpatients at a local research hospital and its outpatient clinic. We expect that the majority of participants early post-stroke will be using wheelchairs for mobility. As such we have designed the equipment they will use to be wheelchair accessible, without requiring transfers. This improves safety and comfort. An occupational therapist will be in the room with the participant during rehabilitation on BAC, to assist as needed. Subjects will not be coerced into participation. The games adapt automatically to each patient's ability and functional level, thus participants will not be at increased risk. They will practice their arms while sitting and their arms will be initially supported during game play when training on the BAC. Biosensors (measuring skin conductance and pulse) will give independent indication of participant's level of stress. Games played by participants will be graded over the duration of rehabilitation.

For the BrightBrainer study on subjects with Parkinson's Disease

- **Number of subjects:** We expect to enrol 2 subjects. They will be living in the community.
- **Gender of Subjects.** We will aim to recruit a male and a female subjects. Due to their age, we do not anticipate a pregnant female to participate.
- **Age of Subjects.** Age between 50 and 80.
- **Racial and Ethnic Origin.** No exclusions will be made due to race or ethnic background.
- **Inclusion Criteria (general)**

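### If the named repeated measures ANOVA is run in its usual complete-case form through the post-outpatient evaluation, the mean gain judged by the 10-point rule describes outpatient completers only

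*Protocol*

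**What the plan says.** Protocol section iii, Data Analysis and Data Monitoring, names one group method: "We will use repeated measures of ANOVA statistical analysis to look at" the data, "comparing pre-training conventional evaluation results with post-training results, to determine early indications of clinical benefit". The paragraph serves the whole protocol. It lists no evaluations, names no arm or arm-by-time term, and gives no rule for missing scores.

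The schedule of the randomised study is under Subject standardised evaluations for control study:
- Around inpatient therapy: "All subjects will be evaluated before, and after their in-patient rehabilitation".
- At the end: "All subjects will be evaluated again at the completion of their outpatient therapy".
- Between these, only subjects who first go home have a pre-outpatient evaluation. For the others, the Emotional & Neuropsychological evaluations section says that "the measures at discharged from inpatient rehabilitation will be considered as baseline for start of outpatient training".

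The outpatient phase lasts 2 to 3 months (Experimental group), and subjects may withdraw at any time (Process of Consent). The controlled-study exclusion criteria give a reason for the 25-mile limit: "Those living too far will have a harder time completing the study as outpatients".

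Under Control study Outcomes, the FMA criterion is that "success will be a group average score increase of 10 points or more, compared to baseline". No post-baseline evaluation is named for it.

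**The concern.** Classical repeated measures ANOVA needs a complete row for each subject. With the post-outpatient score in the model, a subject lost during the outpatient months contributes nothing, not even the baseline and post-inpatient scores. The post-inpatient score is the best available guide to where that subject was heading.

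The FMA criterion is a group mean against a fixed threshold, so it is sensitive to who remains in the mean. If those who did poorly as inpatients are more likely to leave, the remaining mean rises without any subject having improved more. With 10 subjects per arm, one loss is 10% of an arm. Adjusting for baseline would not help, because the same subjects would still be missing.

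**Working it through.** **No figure to reproduce.** The protocol states no SD, alpha, power or dropout rate. The only arithmetic, 10 + 10 = 20, agrees. Everything below except 10 per arm and the 10-point threshold is an assumption.

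**1. What the method does with an incomplete row.** Twenty invented subjects had three evaluations each, and four lacked the last.
- A standard repeated measures ANOVA routine rejected the data as unbalanced. After those four were removed it ran on 16 subjects, with denominator df (16 − 1) × 2 = 30 instead of (20 − 1) × 2 = 38.
- A mixed model on the same data kept all 20 subjects and 20 × 3 − 4 = 56 scores.
- A repeated measures ANOVA of pre- against post-inpatient scores alone kept all 20 (df 19).

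So the loss of subjects depends on the final evaluation being in the model.

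**2. Shift in a completer mean.** Let Z be the standardised inpatient gain, ρ its correlation with the final gain, and SD_F the SD of the final gain. Let the log-odds of loss be a − bZ, with a set to give the stated total loss. With S(z) = 1/(1 + exp(a − bz)) the chance of staying and φ the normal density:

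m = ∫ z S(z) φ(z) dz / ∫ S(z) φ(z) dz, and shift = ρ × SD_F × m.

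With SD_F = 8:

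| b | Lost | m | Shift, ρ = 0.5 | Shift, ρ = 0.7 |
|---|---|---|---|---|
| 0.5 | 21% | 0.101 | 0.40 | 0.57 |
| 1 | 13% | 0.116 | 0.46 | 0.65 |
| 1 | 25% | 0.213 | 0.85 | 1.19 |
| 1 | 34% | 0.284 | 1.14 | 1.59 |

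Simulation with ρ = 0.7, an inpatient-gain SD of 5 and a true mean final gain of 8 gave completer means of 8.9, 9.4 and 9.8 at 15%, 25% and 34% loss. These are shifts of 0.9, 1.4 and 1.8. An estimate that uses the post-inpatient score gave 8.0. The upper figure is not a ceiling: b = 1.5 with 34% lost gives 0.7 × 8 × 0.367 = 2.06.

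**3. Effect on the 10-point rule (true mean gain 8).** With full data, the SE of a mean of 10 is 8/√10 = 2.53, so the chance of a mean of at least 10 is 1 − Φ(2/2.53) = 0.21 (simulated: about 0.22). Simulated with losses:

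| Scenario | Completers | Using post-inpatient score |
|---|---|---|
| Mild (b = 0.5, 21% lost; b = 1, 13% lost) | 0.28–0.31 | 0.22–0.24 |
| 15%, 25%, 34% lost | 0.34, 0.42, 0.47 | 0.24–0.25 |

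**4. Arm difference.** A separate simulation used three evaluations, 10 per arm, SD 10, correlation 0.7 between evaluations, and true final gains of 10 (control) and 15 (experimental), so a true difference of 5. Loss rates are nominal.

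| Loss pattern | Completer means | Completer difference | All-subject difference |
|---|---|---|---|
| 20%, unrelated to early gain | 9.98, 15.01 | 5.03 | 5.04 |
| 20%, poor gainers leave both arms | 10.78, 15.84 | 5.05 | 5.06 |
| 30%, poor gainers leave both arms | 11.10, 16.11 | 5.01 | 5.05 |
| 20%, opposite by arm | 9.21, 15.81 | 6.60 | 5.10 |
| 20%, opposite by arm, reversed | 10.80, 14.20 | 3.40 | 4.91 |
| 30%, opposite by arm | 8.90, 16.14 | 7.24 | 5.28 |

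When loss works the same way in both arms, the means shift by 0.8 to 1.1 points and the difference does not move.

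**5. Precision.** In that simulation at 20% loss, the SD of the estimated difference was 3.90 (completers) against 3.97 (all subjects) under random loss, and 3.96 against 4.52 when poor gainers left both arms. Under the assumptions of step 2, random loss of 20 to 30% and one slope pooled across arms, it was 4.0 to 4.4 against 3.8 to 4.0. No reliable gain in precision can be claimed.

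**The case against.** A reader might infer that the protocol discards every subject without a final score, and that the treatment comparison is therefore biased. The document supports neither statement.

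- **No discarding is stated.** It follows from the usual form of the method. The name does not exclude a likelihood-based fit, and missing-data handling may be set out in an SAP that is not shown. This stands, and it makes the point conditional. What remains is that the one method named suits this schedule poorly in its ordinary form.
- **The final evaluation is not fixed as the contrast.** Post-training could mean post-inpatient, which would keep outpatient dropouts. This also stands. However, the schedule and the planned recovery curves under Control study Outcomes both extend to the end of outpatient therapy.
- **No arm contrast is defined.** The analysis sentence describes before against after, and the FMA criterion is within group. Step 4 shows that the difference moves only when loss relates to early gain differently by arm, and nothing in the document suggests such a pattern.
- **The protocol tries to prevent losses.** The distance criterion and the search at screening for candidates who will continue as outpatients are preventive. They show that non-completion was foreseen as a risk but imply no rate.
- **A mixed model is not free of trouble at this size.** An unstructured covariance over up to four evaluations, one of them optional, can be unstable with 20 subjects. This stands and shapes the fix.

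**Conclusion.** The point holds conditionally. If the ANOVA is run on complete cases through the post-outpatient evaluation and poor inpatient gainers leave more often, the group mean set against 10 points is overstated by about 0.4 to 1.8 points under the assumed SDs, correlations and 13 to 35% loss. A steeper link between early gain and loss would give more; loss unrelated to early gain would give none. For a true mean gain of 8, the chance of meeting the rule rises from about 0.22 to between 0.28 and 0.47. Bias in the arm difference needs differential loss, and better precision is not a reason for the change. The case rests on the within-arm mean, because that is what the protocol judges.

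**What to change.** In Data Analysis and Data Monitoring, for the randomised study, replace repeated measures ANOVA with wording such as: *Scores will be analysed with a linear mixed model for repeated measures using all available evaluations of all randomised subjects, with arm, evaluation and their interaction, a simple covariance structure suited to 20 subjects, and small-sample degrees of freedom. The arm difference and the mean change set against the 10-point criterion will be estimated from this model at [named evaluation].*

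Add that, for subjects who go directly to outpatient therapy, the discharge score serves as the outpatient baseline and is entered once, not twice. The protocol states that convention under the cognitive and emotive evaluations; it should be stated for the motor scores as well.

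The cost is a few sentences and slightly more analysis work, with no new data. The downside is reliance on missing at random given the observed scores and on a parsimonious covariance model. Label: cheap improvement.
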